**6. Use of Controlled Substances:**

Will this research project involve the use of controlled substances in human subjects?

Yes  No See instructions to view controlled substance listings.

If yes, is the use of the controlled substance considered:

Therapeutic: The use of the controlled substance, within the context of the research, has the potential to benefit the research participant.

Non Therapeutic: Note, the use of a controlled substance in a non therapeutic research study involving human subjects may require that the investigator obtain a Laboratory Research License. Examples include controlled substances used for basic imaging, observation or biochemical studies or other non-therapeutic purposes. See Instructions for further information.

**7. Continuation of Drug Therapy After Study Closure  Not applicable to this project**

Are subjects provided the opportunity to continue to receive the study drug(s) after the study has ended?  Yes  No

If yes, describe the conditions under which continued access to study drug(s) may apply as well as conditions for termination of such access.

**SECTION VII: HUMAN SUBJECTS**

**1. Recruitment Procedures:** How will potential subjects be identified, contacted and recruited?

Attach copies of any recruitment materials that will be used.

Flyers  
 Posters  
 Letter  
 Medical Record Review

Internet/Web Postings  
 Mass E-mail Solicitation  
 Departmental/Center Website  
 Departmental/Center Research Boards

Radio  
 Telephone  
 Television  
 Newspaper

Departmental/Center Newsletters  Web-Based Clinical Trial Registries  
 Other (describe):  Clinicaltrials.gov Registry (do not send materials to HIC)

Recruitment will occur by conducting AUDIT-C screenings at the study sites in coordination with the clinical teams. In addition to recruiting through clinics (NSC, West Haven VA, and the Haelen Center), we will recruit at sites that provide services to HIV-infected patients, including AIDS Project New Haven, Hill Health Center, Fair Haven Community Health Center, Hispanos Unidos, and Liberty Housing.

Recruitment via Respondent Driven Sampling (RDS):

In addition to the recruitment methods listed above, a sampling approach termed respondent driven sampling (RDS) will be employed. One of the goals of this approach is to gain more access to subjects that would not ordinarily present for routine medical care. In using RDS, we will attempt to engage our current study participants as active recruiters by way of the provision of incentives. Each study participant will be offered the opportunity to participate in recruitment of other subjects. If they choose not to participate, this in no way will affect their treatment in the study. Those subjects who agree to participate in RDS will each be given 5 coupons, [REDACTED]

[REDACTED] for each enrollee they recruit. To create waves of chain referral, participants are given these coupons to give to other out-of-treatment HIV positive patients with heavy drinking or alcohol abuse/dependence they seek to refer to the study. To protect the confidentiality of all respondents, each participant is assigned a series of unique coupon identification codes, and these codes will be placed on the coupons. These codes will be stored in a secure central database. [REDACTED]

**1.a. Assessment of Current Health Provider Relationship for HIPAA Consideration:**

Does the Investigator or any member of the research team have a direct existing clinical relationship with any potential subject?

Yes, all subjects  
 Yes, some of the subjects  
 No

If yes, describe the nature of this relationship.

Some of the members of the research team may have a clinical relationship with patients who subsequently enroll as subjects in the study.

**2. Subject Population** Provide a detailed description of the targeted involvement of human subjects for this research project.

Participants will be 50 HIV-infected men and women who report heavy drinking, alcohol abuse or dependence. Referrals will come from within the Nathan Smith Clinic HIV clinic sites, via local HIV care sites, website advertisements, local papers, community postings, community physicians, other patients, local mental health centers, local hospitals, and substance abuse treatment facilities.

**3. Inclusion/Exclusion Criteria:** What are the criteria used to determine subject inclusion or exclusion? How will eligibility be determined, and by whom?

**Inclusion criteria:** Each subject must:

1. Be HIV-infected.
2. Be currently prescribed HAART medication.
3. Report less than 95% adherence to their HAART medication.
4. Report heavy drinking 4 or more times in the past 4 weeks, or meets current criteria for alcohol abuse or dependence. Heavy drinking is defined as 4 or more drinks for women and 5 or more drinks for men on an occasion.
5. Be at least 18 years old.
6. Be able to understand English and provide informed consent.

**Exclusion criteria:** No subject may:

1. Be psychotic or severely psychiatrically disabled.
2. Be currently enrolled in formal treatment for alcohol (excluding self-help, e.g. Alcoholics Anonymous)
3. Have medical conditions that would preclude completing or be of harm during the course of the study.
4. Have laboratory or clinical evidence of significant liver dysfunction (alanine aminotransferase (ALT) or aspartate aminotransferase (AST) greater than 5 times the upper limit of the normal range) or cirrhosis with a Child-Pugh classification greater than A or B.
5. Have a known contraindication to NTX therapy (e.g. requiring opioid medication for pain).
6. Be pregnant, nursing or unable to use an effective method of birth control (women).
7. Patients with a positive urine opioid screen result
8. Known hypersensitivity to naltrexone, PLG (polylactide-co-glycolide, carboxymethylcellulose, or any other components of the diluent

Subjects will first be screened by the research assistant and final eligibility will be determined by the Investigators. Research participants will be interviewed by specially trained research assistants, using standardized psychological assessments. Participants will also complete self-report rating forms.

3.a. Will email or telephone correspondence be used to screen potential subjects for eligibility prior to the potential subject coming to the research office?  Yes  No

3.b. If yes, will identifiable health information be collected during this screening process and retained by the research team?  Yes  No

4. **Subject Classifications: Check off all classifications of subjects that will be invited to enroll in the research project.** Will subjects, who may require additional safeguards or other considerations, be enrolled in the study? If so, identify the population of subjects requiring special safeguards and provide a justification for their involvement.

 Children	 Healthy	 Fetal material, placenta, or dead fetus
 Non-English Speaking	 Prisoners	 Economically disadvantaged persons
 Decisionally Impaired	 Employees	 Pregnant women and/or fetuses
	 Students	 Females of childbearing potential

a. Is this research proposal designed to enroll children who are wards of the state as potential subjects?  Yes  No (If yes, see Instructions section VII #4 for further requirements)

## SECTION VIII: CONSENT/ ASSENT PROCEDURES

1. **Consent Personnel:** List all members of the research team who will be obtaining consent/assent.

[name] (Project Director), [REDACTED]

[REDACTED] [name], [name], [name], and [name] (Investigators).

2. **Process of Consent/Assent:** Describe the setting and conditions under which consent/assent will be obtained, including parental permission or surrogate permission and the steps taken to ensure subjects' independent decision-making.

Participants will be recruited through clinical sites, word of mouth, flyers, posters, websites, and advertisements. A phone number will be provided for potential participants to call to arrange an appointment to come speak to a Research Assistant about the study. During this meeting, the research assistant will describe the study in more detail, determine interest in participating, and assess potential eligibility. After fully informing participants about the study and answering any questions, the research assistant will obtain written informed consent from participants for participating in the study and allowing us to complete all baseline evaluations and to assess them throughout the study. Prior to admitting the participant to the treatment phase of the study, all participants will be evaluated by the study physician or nurse who will review all medical and assessment data, review the study protocol with the participant, and discuss the risks and benefits of treatment with VIVITROL. Individuals who do not meet eligibility criteria or who decline to take part in the study will be referred to an appropriate treatment program. Once the subject has signed the consent, they may withdraw consent at any time.

3. **Evaluation of Subject(s) Capacity to Provide Informed Consent/Assent:** Indicate how the personnel obtaining consent will assess the potential subject's ability and capacity to consent to the research being proposed.

This research does not involve subjects with limited decision making capacity.

4. **Documentation of Consent/Assent:** Specify the documents that will be used during the consent/assent process. Copies of all documents should be appended to the protocol, in the same format that they will be given to subjects.

Please see attached consent forms.

5. **Non-English Speaking Subjects:** Explain provisions in place to ensure comprehension for research involving non-English speaking subjects. Translated copies of all consent materials must be submitted for approval prior to use. NA

6. **Waiver of Consent:** Will you request either a waiver of consent, or a waiver of signed consent, for this study? If so, please address the following:

**This section is not applicable to this research project**

Waiver of consent: (No consent form from subjects will be obtained.)

- a. Does the research pose greater than minimal risk to subjects?  Yes  No
- b. Will the waiver adversely affect subjects' rights and welfare?  Yes  No
- c. Why would the research be impracticable to conduct without the waiver?
- d. Where appropriate, how will pertinent information be returned to, or shared with subjects at a later date?

Waiver of **signed** consent: (Verbal consent from subjects will be obtained.)

**This section is not applicable to this research project**

- a. Would the signed consent form be the only record linking the subject and the research?  Yes  No
- b. Does a breach of confidentiality constitute the principal risk to subjects?  Yes  No

**OR**

- c. Does the research pose greater than minimal risk?  Yes  No **AND**
- d. Does the research include any activities that would require signed consent in a non-research context?  Yes  No

7. **Required HIPAA Authorization:** If the research involves the creation, use or disclosure of protected health information (PHI), separate subject authorization is required under the HIPAA Privacy Rule. Indicate which of the following forms are being provided:

Compound Consent and Authorization form  
 HIPAA Research Authorization Form

1. **Request for waiver of HIPAA authorization:** (When requesting a waiver of HIPAA Authorization for either the entire study, or for recruitment purposes only)

**Choose one:** For entire study: \_\_\_\_\_ For recruitment purposes only: \_\_\_\_\_

- 1. Describe why it would be impracticable to obtain the subject's authorization for use/disclosure of this data;
- 2. If requesting a waiver of **signed** authorization, describe why it would be impracticable to obtain the subject's signed authorization for use/disclosure of this data;

**By signing this protocol application, the investigator assures that the protected health information for which a Waiver of Authorization has been requested will not be reused or disclosed to any person or entity other than those listed in this application, except as required by law, for authorized oversight of this research study, or as specifically approved for use in another study by an IRB.**

*Researchers are reminded that unauthorized disclosures of PHI to individuals outside of the Yale HIPAA-Covered entity must be accounted for in the "accounting for disclosures log", by subject name, purpose, date, recipients, and a description of information provided. Logs are to be forwarded to the Deputy HIPAA Privacy Officer.*

**SECTION IX: PROTECTION OF RESEARCH SUBJECTS**

1. **Risks:** Describe the reasonably foreseeable risks, including risks to subject privacy, discomforts, or inconveniences associated with subjects participating in the research.

Naltrexone (NTX): Numerous studies have found NTX to be safe and rarely associated with toxicity or severe side effects. These side effects appear to be dose-related and are less likely to occur at the dose proposed in this study. The most frequently reported side effects are gastrointestinal in nature, including epigastric pain, nausea and vomiting. Other, less frequent side effects include nervousness, headaches, low energy, sweating, joint and muscle pain, blurred vision and insomnia. Hepatotoxicity can occur but typically at much higher doses (e.g., 200-300 mg daily) and resolves when NTX is discontinued. Additionally, case reports have reported elevated liver enzyme tests in patients who were taking non-steroidal anti-inflammatory drugs in combination with high-dose NTX. NTX has been shown to have an effect on the embryo in the rat and the rabbit when given in doses approximately 140 times the human therapeutic dose. Thus, we will not enroll pregnant or nursing women or those who do not agree to use a reliable form of birth control. NTX, as an opioid antagonist, can block the effects of opioids and can precipitate opioid withdrawal in an opioids dependent individual. Thus, we will not enroll opiate dependent individuals, those requiring opioids for analgesia, and those who have a positive urine toxicology test for opioids.

Before FDA approval, extended release naltrexone was studied in more than 900 patients [63]. Extended release naltrexone appears to be generally well tolerated, and adverse effects tend to be mild [61, 110]. Patients using extended release naltrexone do not develop tolerance for or dependence on the medication.

The extended release formula has been shown to be safe, tolerable, and efficacious in the treatment of alcohol use disorders [61]. In this large 6-month multi-site study in the treatment of alcohol dependence the most common adverse events (AEs) were nausea, headache, and fatigue. Other less common AEs included insomnia, vomiting, decreased appetite, diarrhea, dizziness, injection site pain, nasopharyngitis, and upper respiratory tract infection. Nausea was mild or moderate in 95% of cases; however the large majority of these cases occurred only during the first month of treatment. The most common injection site reaction was tenderness. Seven patients (1%) discontinued injections due to site reactions. Study discontinuation secondary to AEs occurred in 29 (14.1%) of the 380mg naltrexone group, 14 (6.7%) of the 190mg group, and 14 (6.7%) in the placebo group. Group differences were accounted for by a greater number of AEs of nausea, injection site reaction, and headache. The percentage of patients who experienced serious AEs (SAEs) was similar among groups (5.4% for 380mg, 4.8% for 190mg, and 7.2% for placebo). The most common SAE was hospitalization for alcohol intoxication. Two SAEs (eosinophilic pneumonia and interstitial pneumonia) were judged as possibly related to study medications. Mean AST and ALT levels did not change significantly over the course of treatment or with medication. A recent large study of extended release NTX found that mean liver enzymes did not change significantly over the course of treatment and there was no effect of medication on the proportion of patients in the different groups who had liver enzyme elevations higher than 3 times the upper limit of normal [61]. In addition, it has been found to be safe for use in patients with mild to moderate liver impairment [109] with evidence of a 15% greater reduction in liver enzyme levels in the NTX group as compared with the placebo group [110].

In a 3-month study of 315 alcohol dependent patients [110] who received monthly injections of NTX, there were no major differences between the NTX group and the placebo group in terms of serious adverse events, adverse events other than injection site reactions, or reactions at the injection site. Six subjects experienced serious adverse events. One subject in the NTX group experienced two such events (i.e., an orbital fracture and a human bite to the face). Five subjects in the placebo group experienced serious adverse events (three subjects were

APPROVED BY THE YALE UNIVERSITY IRB 10/11/2018 VALID THROUGH 10/13/2019  
hospitalized due to alcoholic relapse, one of whom required detoxification and had suicidal depression; one subject required surgical repair of an ulnar fracture; and one subject was hospitalized for cellulitis at the injection site, which resolved within 2 weeks). There was no overall group difference in the percentage of patients reporting one or more adverse events. The most common adverse events were headache, nausea, and fatigue. Three adverse events differed significantly by treatment group: upper abdominal pain was more common in the NTX group, and irritability and chest pain occurred more commonly among placebo subjects. Injection site adverse events occurred at an overall frequency of 5% and this rate differed significantly by group. A significantly greater percentage of subjects in the NTX group reported one or more injection site reactions. The most common injection site reactions were pain, induration, and contusion, with a trend for pain to be more common in the NTX group.

While there is an inherent risk of precipitating alcohol withdrawal in any patient with alcohol dependence who seeks medical treatment, VIVITROL does not itself increase the risk of alcohol withdrawals. Alcohol withdrawal syndromes are not listed as known adverse reactions to this medication, nor is there any physiologic mechanism by which VIVITROL should precipitate withdrawal, insofar as VIVITROL has no direct alcohol antagonistic effects. Moreover, the current proposal emphasizes *cutting back* on drinking, rather than abstinence, which further attenuates any theoretical risk of alcohol withdrawal. Thus, while each subject is followed closely by a physician or nurse practitioner throughout the course of the study, no additional monitoring for alcohol withdrawal is indicated. Nonetheless, patients will be cautioned regarding the signs and symptoms of alcohol withdrawal syndromes, and will be provided relevant emergency contact information in the event that they begin to experience such symptoms. Should they experience symptoms of alcohol withdrawal patients will be instructed to seek emergency medical care without delay and to contact the study team as soon as they are able.

While the concern for NTX's hepatotoxicity appropriately warrants monitoring of liver function, theoretically and based on the minimal existing literature on interactions between NTX and HAART, these interactions should be clinically insignificant. Many of the medications used for the treatment of HIV are metabolized via the cytochrome P-450 system (CYP450) leading to issues surrounding drug interactions with a number of medication classes. The metabolism of NTX, however, is not entirely metabolized via CYP450 and therefore significant interactions with HAART medications would not be expected [111, 112]. The first step of NTX metabolism involves hydroxylation which likely involves the CYP450 system. The second step, glucuronidation, does not involve the CYP450 system. These findings would indicate that given the hydroxylation step being CYP450-dependent, it is important to monitor for interactions with the non-nucleoside reverse transcriptase class of HIV medications as well as being vigilant to the fact that patients with impaired hepatic function due to HCV or alcohol dependence. One study evaluating the effect of opioid medications on the disposition of the antiretroviral medication zidovudine (AZT) found that NTX had no significant effect on the area under the curve, maximal concentration or half-life of AZT [113]. In turn, another study suggested that NTX might potentiate the antiviral effects of AZT and one of the protease inhibitors Indinavir, increasing their antiviral activity 2-3 fold [9]. In addition, a large multi-center safety study of the use of NTX for alcoholism in 865 individuals, including patients with comorbid psychiatric illness, concomitant medications, polysubstance abuse, and HIV demonstrated that serious side effects in these populations were uncommon [115]. While this study was not randomized in design and was intended to look at medication interactions, the findings are reassuring for patients with HIV disease. Extended release naltrexone is approved for use in patients who meet criteria for Childs-Pugh A and B liver disease. While these data are reassuring, monitoring of liver function, to assess for

APPROVED BY THE YALE UNIVERSITY IRB 10/11/2018 VALID THROUGH 10/13/2019  
hepatotoxicity, will be important, especially in HIV/HCV co-infected patients. The proposed study will systematically examine the question of medication interactions by closely following for adverse effects.

To examine antiretroviral and hepatic safety in HIV-infected patients receiving naltrexone we conducted an analysis of the NIAAA-funded VACS Virtual Cohort. All patients were receiving antitretroviral medications. The median duration of naltrexone treatment for the cohort was 90 days. We compared CD4 cell count, HIV viral load (VL), AST and ALT during the period in which patients had received a prescription for naltrexone. We compared baseline and follow-up laboratory results using descriptive statistics and Wilcoxon signed-rank tests. The results are included in the table below.

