## **Participants**

### Sample size estimation

A total of 154 participants will be enrolled at the three participating clinics. The following assumptions were used to derive this sample size:

Proportion of Placebo+MM/MC participants achieving >95% adherence = 20%

Proportion of Vivitrol+MM/MC participants achieving >95% adherence = 40%

Power=72%

Alpha level=0.05

Participants at the Nathan Smith Clinic will be 50 HIV-infected men and women who report heavy drinking, alcohol abuse or dependence. Referrals will come from within the Nathan Smith Clinic site, via local HIV care sites, website advertisements, local papers, community postings, community physicians, other patients, local mental health centers, local hospitals, and substance abuse treatment facilities.

***Inclusion criteria:*** Each subject must:

1. Be HIV-infected.
2. Currently be prescribed HAART medication.
3. Report less than 95% adherence to their HAART medication.
4. Report heavy drinking 4 or more times in the past 4 weeks, or meet current criteria for alcohol abuse or dependence. Heavy drinking is defined as 4 or more drinks for women and 5 or more drinks for men on one occasion.
5. Be at least 18 years old.
6. Be able to understand English and provide informed consent.

***Exclusion criteria:*** No subject may:

1. Be psychotic or severely psychiatrically disabled.
2. Be currently enrolled in formal treatment for alcohol (excluding self-help, e.g. Alcoholics Anonymous)
3. Have medical conditions that would preclude completing or be of harm during the course of the study.
4. Have laboratory or clinical evidence of significant liver dysfunction (alanine aminotransferase (ALT) or aspartate aminotransferase (AST) greater than 5 times the upper limit of the normal range) or cirrhosis with a Child-Pugh classification greater than A or B.
5. Have a known contraindication to NTX therapy (e.g. requiring opioid medication for pain).
6. Be pregnant, nursing or unable to use an effective method of birth control (women).
7. Patients with a positive urine opioid screen result
8. Known hypersensitivity to naltrexone, PLG (polylactide-co-glycolide, carboxymethylcellulose, or any other components of the diluent

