Randomization: Eligible participants will be randomly assigned to VIVITROL + MM/MC or placebo + MM/MC by the investigational pharmacist. All staff, other than this individual and the study biostatistician(s), will be blind to treatment allocation. Subjects will be assigned to one of the two conditions using stratified randomization. There will be 6 strata: (a) participating clinic (3) and (b) alcohol abuse/dependence (Yes/No; 2) in the randomization scheme.

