### ***Treatment***

#### Medication: VIVITROL versus placebo:

Medication: VIVITROL versus placebo: Participants will receive either active VIVITROL or placebo throughout the 24-week treatment period; they will be told that they have a 50% chance of receiving the active drug. Those assigned to the VIVITROL arm will receive monthly extended release VIVITROL doses at 380mg (4 mL), administered as an intramuscular gluteal injection at 4-week intervals. Consistent with prior studies [60], we will encourage patients to be abstinent from alcohol use for four days or more prior to receiving the dose of extended release VIVITROL. We chose the 380mg dose because it was found in a recent randomized trial to be more efficacious than a 190mg dose with no significant differences in side effects or rates of hepatotoxicity. For the placebo arm of the study, patients will be dosed in a similar manner receiving 4 mL injections of placebo at 4-week intervals. All active and placebo doses will be administered by the study nurse.

Counseling Intervention: Our compound counseling intervention will consist of two efficacious, manualized behavioral treatments intended to augment VIVITROL's effects: Medical Management (MM) and Medication Coaching (MC). MM is a manual-guided supportive counseling therapy with demonstrated effectiveness (see the COMBINE Study [10], Appendix B). This treatment incorporates the clinical skills and advice used by primary

APPROVED BY THE YALE UNIVERSITY IRB 10/11/2018 VALID THROUGH 10/13/2019  
care practitioners supplemented with referrals for all patients to Alcoholics Anonymous. The initial MM visit will consist of: discussion of medical concerns, information on VIVITROL, assessment of medication compliance, provision of written educational materials on alcohol problems and treatment, and a question/answer period. The core elements covered at each follow-up MM visit are: 1) Medical status, medication safety, medication adherence, 2) Drinking status, and 3) Troubleshooting based on patients' drinking and medication adherence status. Each follow-up visit will include approximately 10-15 minutes of MM counseling.

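### Does the advice to abstain before the injection undercut the protocol's reasons for adding no alcohol-withdrawal monitoring?

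*Combined protocol and SAP*

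**What the plan says.** The Risks text in Section IX, item 1 opens its paragraph on alcohol withdrawal by accepting that "there is an inherent risk of precipitating alcohol withdrawal in any patient with alcohol dependence who seeks medical treatment". It then gives reasons why the study drug adds nothing to that risk: it does not itself raise it, withdrawal is not a listed reaction, and no mechanism is known. A further reason follows, about behavior rather than the drug. The proposal emphasizes cutting back on drinking "rather than abstinence, which further attenuates any theoretical risk of alcohol withdrawal". The conclusion, set against close follow-up by a physician or nurse practitioner, is that "no additional monitoring for alcohol withdrawal is indicated". The paragraph ends with safeguards: patients are warned about signs and symptoms and given emergency contacts, and if symptoms occur "patients will be instructed to seek emergency medical care without delay and to contact the study team as soon as they are able".

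The treatment description in Section V, item 3 (*Medication: VIVITROL versus placebo*) says, with a citation to an earlier analysis of extended-release naltrexone, that "we will encourage patients to be abstinent from alcohol use for four days or more prior to receiving the dose of extended release VIVITROL". It does not say which injection is meant.

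Inclusion criterion 4 admits people who report heavy drinking "or meet current criteria for alcohol abuse or dependence". Randomization is stratified by clinic and by "alcohol abuse/dependence (Yes/No; 2) in the randomization scheme". All staff except the investigational pharmacist and the study biostatistician(s) "will be blind to treatment allocation".

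**The concern.** A safety statement should rest on what the trial actually asks of patients. Here one stated reason is that the trial does not press for abstinence, while the treatment section encourages a stop of four days or more. By the Risks paragraph's own logic, an abrupt stop is when its reassurance about cutting back would be least applicable.

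The other reasons do not obviously fill the gap. They concern the drug, and withdrawal from stopping drinking is not a drug effect. Because treating staff are blinded, the advice cannot sensibly be given to one arm only, so the question would arise in both arms. The group in which the protocol itself acknowledges the risk is enrolled by design and is a stratification factor.

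If the no-monitoring conclusion depended on the cutting-back reason, an ethics committee would have approved it on a description of the trial that another section does not bear out. That would be worth correcting.

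**Working it through.** There is no figure to reproduce and no formula to apply. The only number in the advice is the four days. The check sets the two texts side by side and asks what remains if the disputed reason is removed.

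**1. Do the statements contradict each other?**

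| | Risks, Section IX item 1 | Treatment, Section V item 3 |
|---|---|---|
| Subject | What the proposal emphasizes overall | What patients are encouraged to do before a dose |
| Duration | The whole trial | Four days or more |
| Force | A treatment aim | Encouragement, not a requirement |

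Both can be true: a trial can aim at reduced drinking and still suggest a brief pause before dosing. The background (*Why NTX and not other alcohol pharmacotherapies?*) fits the reduction aim. It says naltrexone may suit drinkers whose goal is not abstinence and can be started in people who are still drinking. What is missing is a sentence linking the two.

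**2. Which dose is meant?** With 24 weeks of treatment and a 4-week interval there are 24 / 4 = 6 injections, and Table 1 agrees (weeks 0, 4, 8, 12, 16, 20). The source cited for the advice is described in the background as concerning abstinence before treatment began, and its title in the reference list says the same. The first injection is therefore the natural reading, although the treatment section does not state it.

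**3. What remains without the cutting-back reason?** The sentence is worded as an addition: it says the risk is attenuated further. Without it, three things still stand:

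- the drug-based reasons;
- the opening acknowledgment of risk in dependent patients, which shows that withdrawal unrelated to the drug was considered;
- the follow-up, the warnings, the emergency contacts and the instruction to seek care.

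The drug-based reasons do not speak to stopping drinking. The safeguards do, because they are triggered by symptoms whatever the cause.

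**4. What is in place around the first injection?** Breathalyzer, SAFTEE and counseling are scheduled at all six injection visits, but those visits say little about the days before the first one. What comes earlier is:

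- history, physical examination, SCID and AUDIT at Week -1 (Table 1), the SCID identifying past or present alcohol use disorders;
- evaluation of every participant by the study physician or nurse before the treatment phase, with review of all medical and assessment data and discussion of risks and benefits (Section VIII, item 2);
- exclusion of people with medical conditions that would be of harm during the study (exclusion criterion 3).

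None of these is withdrawal monitoring as such. They do put a clinician's review of the individual patient before the start of treatment.

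**5. Does the point reach the comparison of arms?** No. If the advice concerns the first injection, it precedes any exposure to study drug. Treating staff are blinded and the randomization is stratified on abuse/dependence, so nothing in the advice should differ by arm. No endpoint, analysis model or sample-size input uses it.

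**The case for a change.** The strongest case for a change is about timing. If the advice concerns the first injection, the encouraged days come just before Week 0. Table 1 has no visit between Week -1 and Week 0, so the breathalyzer, SAFTEE and counseling at Week 0 come at the end of the pause, not during it. The Risks paragraph does not say when patients receive the warnings. The cutting-back reason is also the only one of its reasons about drinking behavior. Nor is the abstinence advice an isolated phrase: all patients are referred to Alcoholics Anonymous, and the counseling includes strategies for engaging patients in abstinence-oriented support groups. A short wording amendment would cost little.

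Part of this stands. The Risks paragraph does omit the pre-dose advice, the schedule has no contact in that interval, and the treatment section leaves the injection unspecified. It is also an inference, though a reasonable one, that the advice reaches both arms, because the sentence names the active product.

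What does not follow is that the conclusion on monitoring is wrong. Rewording the rationale would leave every procedure, safeguard and analysis as it is, because the level of monitoring would remain the investigators' decision. The counseling manuals and consent forms, where the advice and the warnings would be given to patients, are not among the documents. The absence of a link in the protocol text therefore does not show that patients receive no linked information.

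**Conclusion.** The mismatch in wording is real but minor. One supplementary reason in the Risks paragraph does not take account of four or more days of encouraged abstinence described in the treatment section. It is an incomplete rationale, not a design fault, and no change to the plan follows.

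This rests on three readings: that the emphasis on cutting back describes the trial's overall aim, that the pre-dose pause is voluntary as written, and that it most naturally concerns the first of six injections. If the investigators meant every injection, the pause would recur, but the safeguards in the Risks paragraph would apply in the same way, and breathalyzer, SAFTEE and counseling would already have begun before each later pause.

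The size cannot be put as a number of patients, because the documents give no withdrawal rate, no uptake of the advice and no count of dependent participants. Whether the monitoring is clinically sufficient is for the investigators, and no view is taken here on it or on the advice itself. The two sections should read consistently. A cross-reference reconciling them, and naming the injection or injections meant, is housekeeping for the next time the document is opened for another reason.
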